#### 3.3 Informed Consent Process

All subjects must be provided a consent form describing the study with sufficient information for subjects to make an informed decision regarding their participation. Subjects must sign the IRB approved informed consent prior to participation in any study specific procedure. The subject must receive a copy of the signed and dated consent document. The original signed copy of the consent document must be retained in the medical record or research file.

#### 3.4 Study Timeline

#### **Primary Completion:**

It is anticipated that the study will reach primary completion (30 days after final subject completes treatment with study agents) 24 months from the time the study opens to accrual.

#### **Study Completion:**

It is anticipated that the study will reach study completion (final date on which data are collected) 36 months from the time the study opens to accrual.

#### 4. TREATMENT PLAN

Potential subjects who preliminarily meet inclusion criteria and exclusion criteria as determined by study staff (for example, the investigator or clinical research coordinator) will meet with study staff to review the study and informed consent in detail. At this time, inclusion and exclusion criteria will be confirmed with the subjects and treating clinicians as necessary.

All eligible subjects (meeting criteria described in Section 3) will receive the drug combination of infigratinib with tamoxifen. Once a dose level for infigratinib is determined, Cohort 1 will close.

All subjects in whom a research biopsy of a disease site is deemed feasible and safe by the investigator will be required to undergo a biopsy to donate 4 to 8 cores of tumor tissue before and on-treatment to be used for research purposes, including genomic/transcriptomic/proteomic analysis and organoid culture derivation as described in Section 2.6. The on-treatment biopsy is recommended to occur on Day 15 of treatment, but any time on treatment is acceptable. Tissue will be transported to the [name] lab for processing and analysis. Subjects who require a tumor biopsy for eligibility assessment will undergo the collection of tissue cores for research simultaneously, whenever possible. Archival tumor tissue, including stored at Stanford University and at other institutions, may be obtained for use for tissue correlative studies as well. Only tissue not needed for diagnostic purposes will be used for research.

Subjects in Cohort 1 will receive tamoxifen 20 mg orally continuously starting on Day 1 and will additionally receive infigratinib orally daily 3 weeks on, 1 week off (28-day cycle) at the dose level dictated by study protocol (125 mg, 100 mg, or 75 mg).

Subjects will continue receiving cycles as above until 18 months on treatment, progression, or unacceptable toxicity (or other reasons outlined in Section 4.3). If toxicity is deemed per the investigator to be related to endocrine therapy (tamoxifen) and not infigratinib, subjects will be given the option of continuing infigratinib only (without endocrine therapy) until progression.

Details on study procedures during Screening, Treatment, and Post-Treatment are provided in the Study Calendar and footnotes (Section 9).

# 4.1 General Concomitant Medication and Supportive Care Guidelines

#### 4.1.1 Concomitant Medication

Administration of other anticancer therapies within 2 weeks of enrollment, except ongoing administration of a bisphosphonate drug or denosumab as treatment for bone metastasis or ongoing administration of a luteinizing hormone-releasing hormone agonist (such as goserelin acetate or leuprolide acetate) or other endocrine therapy, is prohibited.

Palliative radiotherapy on study is permitted for the treatment of painful bony lesions providing the lesions were known at the time of study entry and the investigator clearly indicates that the need for palliative radiotherapy is not indicative of disease progression. In view of the current lack of data about the interaction of infigratinib with radiotherapy, infigratinib treatment should be interrupted during palliative radiotherapy, resuming infigratinib treatment after recovery to ≤ Grade 1 radiotherapy-related toxicity.

Details for specific medications prohibited while on study are provided in Appendix A. The rationale for the restricted medications is provided below.

Strong inhibitors of CYP3A4 such as the ones listed in Appendix A are prohibited because infigratinib is a likely substrate of this isoenzyme.

Strong inducers of CYP3A4 are prohibited because their usage may decrease the exposure of infigratinib. Therefore, agents such as those listed in Appendix A are prohibited. Please note that the list may not be exhaustive.

Subjects must also avoid the consumption of grapefruits; grapefruit juice; grapefruit hybrids; pomegranates; star fruits; pomelos; Seville oranges; or juice within 7 days prior to the first dose of infigratinib and throughout the treatment period due to a potential CYP3A4 interaction with study drug.

Medications that increase the serum levels of phosphorus and/or calcium are prohibited.

Preliminary clinical data have shown that infigratinib has no effect on cardiac conduction or ECG intervals (See current version of the infigratinib Investigator's Brochure). However, medications that are known to prolong the QT/QTc interval or induce TdP (risk of TdP/QT prolongation) are prohibited. List of these medications is given in Appendix A. Please note that the list might not be comprehensive.

Medications that are allowed but should be administered with caution are provided in Appendix B. The rationale for these medications is provided below.

Infigratinib is characterized by pH-dependent solubility, and therefore, medicinal products that alter the pH of the upper GI tract may alter the solubility of infigratinib, and limit bioavailability. These agents include, but are not limited to, proton pump inhibitors (eg, omeprazole), H2-antagonists (eg, ranitidine) and antacids. If possible, proton pump inhibitors should be avoided due to their long PD effect and replaced with  $H_2$ -antagonists or antacids. Study drug should be taken  $\geq 2$  hours before or 10 hours after dosing with a gastric protection agent.

Infigratinib is a substrate of CYP3A4. Therefore, moderate inhibitors and inducers should be used with caution if an alternative is not available. If anticoagulation is required, heparin and/or low-molecular-weight heparins or direct thrombin inhibitors and/or Factor Xa inhibitors that are not metabolized by CYP3A4 (eg, dabigatran, edoxaban) are preferred. If unavoidable, anticoagulants that are CYP3A4 substrates and have a narrow therapeutic index [eg, warfarin sodium or any other coumadin-derivative anticoagulants or certain direct thrombin inhibitors (eg, argatroban or Factor Xa inhibitors, eg, rivaroxaban)] should be used with caution.

Infigratinib was shown in vitro to inhibit the drug transporter breast cancer resistance protein (BCRP), with an IC50 of 210 nM. While the clinical relevance of this inhibition is unknown, drugs transported by BCRP should be used with caution.

Anti-emetics are recommended as clinically appropriate at the first sign of nausea and vomiting or as prophylaxis to prevent emesis, along with supportive care according to clinical practice guidelines.

It is recommended to avoid using drugs that are known to cause QT prolongation. Note that some anti-emetics have a known risk for Torsade de Pointes, and therefore need to be used with caution. See Appendix B for list of drugs that need to be used with caution. Aprepitant (brand name: Emend) is both a sensitive substrate and a moderate CYP3A4 inhibitor and should be used with caution if an alternative is not available.

Preliminary clinical data have shown that infigratinib has no effect on cardiac conduction or ECG intervals (see current version of the infigratinib Investigator's Brochure). However, medications that have the potential to prolong the QT/QTc interval or induce Torsade de Pointes (possible and conditional risk of TdP/QT prolongation) are allowed with caution. Investigators at their discretion may co-administer such medications, but subjects should be carefully monitored. See Appendix B for list of drugs that need to be used with caution. Please note that the list might not be comprehensive.

Otherwise, concomitant treatment considered necessary for the subject's well-being may be given at discretion of the treating physician. All concomitant medications (including herbal supplements and vitamins), blood products, as well as interventions (eg, paracentesis, etc.) received by subjects from screening until the end of study visit will be recorded in the CRF.

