8.	Has consumed grapefruit, grapefruit juice, grapefruit hybrids, pomegranates, star fruits, pomelos, Seville oranges, or products containing juice of these fruits within 7 days prior to first dose of study drug.			
9.	Have used amiodarone within 90 days prior to first dose of study drug.			
10.	Has used medications known to prolong the QT interval and/or are associated with a risk of Torsades de Pointes (TdP) 7 days prior to first dose of study drug. See Appendix A for a list of prohibited concomitant medications and supplements.			

Prospective Participants Must NOT Match ANY of These Exclusion Criteria	Yes	No	Supporting Documentation *
11. Has used calcium or vitamin D within 3 days prior to first dose of study drug. Calcium supplementation may subsequently be used as clinically indicated (for hypocalcemia) on study.			
12. Have clinically significant cardiac disease including any of the following:			

 
a. Congestive heart failure requiring treatment (New York Heart Association Grade ≥ 2), left ventricular ejection fraction (LVEF) < 50% or local lower limit of normal as determined by multiple gated acquisition (MUGA) scan or echocardiogram (ECHO), or uncontrolled hypertension (refer to the European Society of Cardiology and European Society of Hypertension guidelines [Williams et al., 2018])
 
b. Presence of Common Terminology Criteria for Adverse Events (CTCAE) v5.0 Grade ≥ 2 ventricular arrhythmias, atrial fibrillation, bradycardia, or conduction abnormality
 
c. Unstable angina pectoris or acute myocardial infarction ≤ 3 months prior to first dose of study drug
 
d. Corrected QT interval-Fredericia (QTcF) > 470 msec (males and females). Note: If the QTcF is > 470 msec in the first electrocardiogram (ECG), a total of 3 ECGs separated by at least 5 minutes should be performed. If the average of these 3 consecutive results for QTcF is ≤ 470 msec, the subject meets eligibility in this regard.
 
e. Known history of congenital long QT syndrome
 
			
13. Have had a recent (≤ 3 months) transient ischemic			
attack or stroke.			
14. Pregnant or nursing			

\* All subject files must include supporting documentation to confirm subject eligibility. The method of confirmation can include, but is not limited to, laboratory test results, radiology test results, subject self-report, and medical record review.

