#### 4.1.2 Supportive Care Guidelines

Any palliative and supportive care for disease related symptoms, including any medication or therapy for a concurrent medical condition are permitted, except if specifically prohibited below.

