#### Management of Hyperphosphatemia

Hyperphosphatemia is a recognized on-target effect of potent and selective inhibitors of the FGFR pathway.

The goal of a low-phosphate diet, when one is recommended per management strategy below, is to restrict dietary phosphate to 600 to 800 mg/day by avoiding high-phosphate foods. High-phosphate foods include dairy products; meats, nuts, and other high-protein foods; processed foods; and dark colas. In general, subjects will be instructed to liberalize their diet on days they are not taking infigratinib (including Days 22 to 28, and during interruption of infigratinib for indications other than hyperphosphatemia), unless their serum phosphorus is currently > 5.5 mg/dL. Similarly, subjects who are taking sevelamer (phosphate-lowering medication) will be instructed to hold it on days they are not taking infigratinib (including Days 22 to 28, and during interruption of infigratinib for indications other than hyperphosphatemia), unless their serum phosphorus is currently > 5.5 mg/dL.

Below is the recommended management strategy for hyperphosphatemia. Section 6 also outlines instructions for when to interrupt and/or dose-reduce infigratinib in addition to these recommendations for management. Notably, these instructions for increased monitoring of serum phosphorus, interruption, and dose reduction begin if serum phosphorus > 7.0 mg/dL.

All subjects will have a serum phosphorus checked on C1D4:

- If serum phosphorus > 5.5 and ≤ 7.0 mg/dL, subjects will be instructed to follow a low-phosphate diet and to take sevelamer 800 mg orally 3 times daily with meals.
- If serum phosphorus > 7.0 mg/dL, subjects will be instructed to follow a low-phosphate diet and to take sevelamer 1200 mg orally 3 times daily with meals.

All subjects will have a serum phosphorus checked on Cycle 1 Day 15:

- For subjects who are not currently following a low-phosphate diet or taking sevelamer:
  - If serum phosphorus > 5.5 and ≤ 7.0 mg/dL, subjects will be instructed to follow a low-phosphate diet and to take sevelamer 800 mg orally 3 times daily with meals.
  - If serum phosphorus > 7.0 mg/dL, subjects will be instructed to follow a low-phosphate diet and to take sevelamer 1200 mg orally 3 times daily with meals.
- For subjects who are currently following a low-phosphate diet and taking sevelamer:
  - o If serum phosphorus < 5.0 mg/dL, subjects will be given the option of liberalizing their diet or stopping the sevelamer (not both).

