### **APPENDICES**

# APPENDIX A: List of prohibited medications and substances

Category	Drug Names	
Strong inhibitors of CYP3A4	clarithromycin, conivaptan, fluconazole, fluvoxamine, indinavir, itraconazole, ketoconazole, lopinavir, mibefradil, miconazole, nefazodone, nelfinavir, norfloxacin, posaconazole, ritonavir, saquinavir, telithromycin, voriconazole	
	grapefruit, grapefruit juice, grapefruit hybrids, pomegranates, star fruits, pomelos, Seville oranges or products containing juice of these fruits	
Strong inducers of CYP3A4	avasimibe, carbamazepine, nevirapine, phenobarbital, phenytoin, pioglitazone, primidone, rifabutin, rifampin, St. John's wort, troglitazone	
Medications which increase serum phosphorus and/or calcium	calcium, parathyroid hormone, phosphate, vitamin D (including multivitamins containing vitamin D)	
Medications with established potential for QT prolongation or TdP	amiodarone, anagrelide, arsenic trioxide, astemizole (off US market), azithromycin, bepridil (off US market), chloroquine, chlorpromazine, cisapride (off US market), citalopram, clarithromycin, cocaine, disopyramide, dofetilide, domperidone (not on US market), dronedarone, droperidol, erythromycin, escitalopram, flecainide, halofantrine, haloperidol, ibutilide, levofloxacin, levomethadyl (off US market), mesoridazine (off US market), methadone, moxifloxacin, pentamidine, pimozide, probucol (off US market), procainamide (oral off US market), quinidine, sevoflurane, sotalol, sparfloxacin (off US market), sulpiride (not on US market), terfenadine (off US market), thioridazine, vandetanib	

Abbreviations: CYP – cytochrome P; TdP – Torsades de Pointes; US – United States.

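### Phosphate is prohibited on study with no written exception for hypophosphatemia, although calcium, on the same list, may be given for hypocalcemia

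*Combined protocol and SAP*

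**What the plan says.** **The ban.** Section 4.1.1: "Medications that increase the serum levels of phosphorus and/or calcium are prohibited". The same section refers to Appendix A for the list and gives its duration: "Details for specific medications prohibited while on study are provided in" that appendix. The relevant Appendix A entry reads "calcium, parathyroid hormone, phosphate, vitamin D (including multivitamins containing vitamin D"), with no qualifier on any item. Exclusion 7 bars subjects who receive, or plan to receive, the same class of drug.

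**The one exception.** Exclusion 11, on calcium and vitamin D before the first dose, adds: "Calcium supplementation may subsequently be used as clinically indicated (for hypocalcemia) on study". Section 4.1.1 and Appendix A do not repeat it, and there is no matching sentence for phosphate.

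**General permissions.** Section 4.1.1 closes by saying that other necessary treatment "may be given at discretion of the treating physician"; that sentence opens with 'Otherwise'. Section 4.1.2 begins by saying that supportive care and treatment of concurrent conditions "are permitted, except if specifically prohibited below".

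**Phosphate-lowering measures.** The recommended hyperphosphatemia scheme in Section 4.1.2 has this row for subjects already on both diet and sevelamer at Cycle 1 Day 15: "If serum phosphorus < 5.0 mg/dL, subjects will be given the option of liberalizing their diet or stopping the sevelamer (not both"). The same section relaxes the diet when the drug is not being taken: "subjects will be instructed to liberalize their diet on days they are not taking infigratinib". It holds sevelamer on those days too. Both instructions cover Days 22–28 and interruptions for reasons other than hyperphosphatemia, unless phosphorus is above 5.5 mg/dL.

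**The concern.** Calcium and phosphate sit on one prohibited line, and only calcium has a route back for a subject who becomes deficient. A careful investigator would conclude that phosphate stays banned even when a subject's phosphorus is low. The choice is then to replace phosphate and record a deviation, or to follow the text and withhold it.

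The deficiency is foreseeable. The study drug disturbs phosphorus in both directions, and the plan adds a low-phosphate diet and a binder for some subjects. Hypophosphataemia has also been serious with this drug: Table 3 records it as an SAE in 3 of 433 subjects, and Section 7.1.1 lists one hypophosphatemia/hypocalcemia episode among the suspected unexpected SAEs.

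A smaller matter is the Cycle 1 Day 15 row, which has no lower bound. Followed literally, it gives 1.5 mg/dL the same response as 4.9 mg/dL: relax one measure and keep the other.

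**Working it through.** **1. Does any clause lift the ban?**

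| Text | Reach | Lifts the ban on phosphate? |
|---|---|---|
| Exclusion 11 | Calcium, for hypocalcemia | No; phosphate not mentioned |
| Discretion clause, end of 4.1.1 | Treatment not already dealt with ('Otherwise') | No |
| Opening of 4.1.2 | Care not prohibited 'below' | Unclear. The ban stands above, in 4.1.1, and nothing later in 4.1.2 prohibits phosphate, but Appendix A comes later in the document and names it |
| Table 6, Grade 3 QTcF | Appropriate electrolyte replacement; the examples are low potassium and low magnesium | At most within that one event |
| Table 6, other clinically significant AEs | Grade 3: hold, then reduce; discontinue if unresolved at 14 days. Grade 4: discontinue | No; it acts on infigratinib, while the list applies throughout the study |

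Two rows leave room for argument. Neither gives an investigator clear permission.

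**2. Background frequency (Section 2.2.9, monotherapy at 125 mg, all causes).** The protocol's totals reproduce from the columns.

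- Table 1, any grade: 22 + 10 + 21 = 53; 53/433 = 12.2%.
- Table 2, Grade 3–4: 14 + 7 + 12 = 33; 33/433 = 7.6%. The next rows are hyponatraemia, 30/433 = 6.9%, and hyperphosphataemia, 29/433 = 6.7%.
- Table 3, serious: 2 + 1 + 0 = 3; 3/433 = 0.7%.
- Grade 3–4 share: 33/53 = 62%. The other 53 − 33 = 20 subjects (20/433 = 4.6%) fall outside the Grade 3–4 rows of Table 6.
- Hypocalcaemia has no row in Tables 1, 2 or 3. Those tables have reporting thresholds (10%, 1.0% and 0.5%), so this means less frequent, not absent.

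**3. Scale in this trial, under an assumption.** If the monotherapy rates held for the combination at its planned doses, the chance of at least one case in n subjects is 1 − (1 − p)^n. The plan allows 3 to 12 evaluable subjects.

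| | p | n = 3 | n = 6 | n = 12 |
|---|---|---|---|---|
| Any grade | 53/433 | 32% | 54% | 79% |
| Grade 3–4 | 33/433 | 21% | 38% | 61% |

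This is the chance of a case, not of a case that needs phosphate. The documents give no rate for the latter.

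**4. How long the Day 15 row governs.** It matters from the draw to the last dosing day, Day 21: 21 − 15 + 1 = 7 days. With the ±3-day visit window, a Day 12 draw gives 21 − 12 + 1 = 10 days and a Day 18 draw gives 21 − 18 + 1 = 4. Inclusion 13 requires 2.5 to 4.5 mg/dL at entry, so every value in the entry range, and every value under it, falls within the row.

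**The case against.** The strongest reply is that the text is less absolute than it looks. Read literally, the opening of Section 4.1.2 permits treatment of a concurrent condition, because the prohibition lies above it. Table 6 also contains a duty to correct electrolytes. This stands in part: a reader might infer that every use of phosphate is certainly a deviation, and the documents do not support that degree of certainty. They support an ambiguous text whose plain reading is a ban, and that still needs correcting.

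Second, the protocol already acts on many of the cases that matter. A possibly related Grade 3 event leads to a hold, during which diet and sevelamer are both released; Grade 4 means discontinuation; and food rich in phosphate is not banned as a medication. This stands as mitigation. It does not cover lower grades or unrelated events, and removing a phosphate-lowering measure is not the same as replacing phosphate.

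Third, a restrictive default has a rationale. Hyperphosphatemia is the commonest adverse event (61.2%). Table 7 counts sustained or marked hyperphosphatemia, and new ectopic calcification of any grade, as DLTs. An open-ended permission could push subjects toward those criteria. This stands, and the remedy should carry conditions.

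Fourth, the Day 15 row belongs to a recommended scheme and lasts a few days. That is right, and the point is minor.

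**Conclusion.** The gap is real and modest. Phosphate is prohibited throughout the study with no written exception. The one exception on that line goes to calcium, for a condition that appears in none of the three safety tables, while hypophosphataemia appears in all three and heads the Grade 3–4 table (33/433, 7.6%). On the plain reading, replacement would be a deviation, and the clauses that might rescue it are ambiguous or confined to one cardiac event. This is a subject-safety and compliance matter that should be corrected.

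Three stronger inferences are not supported. The documents do not link the reported hypophosphataemia events to binders, diet or withheld phosphate, so no harm can be attributed to this wording. They give no basis for a change in the DLT count, sample size or dose decision. The list for management after Cycle 1 is silent at or below 5.5 mg/dL and does not stop an investigator from stepping down, so no defect is claimed there.

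The textual conclusion rests on no numerical assumption. The frequencies are monotherapy background rates, and the step-3 probabilities depend on carrying them over to this combination.

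**What to change.** **Main change.** Add to Section 4.1.1, and as a note to Appendix A, that phosphate may be given as clinically indicated for documented hypophosphatemia once sevelamer and the low-phosphate diet have been stopped, and is itself stopped when serum phosphorus is back to normal. Repeat the Exclusion 11 calcium exception beside it, so that both exceptions stand with the ban.

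**Minor change.** Limit the one-measure-only rule in the Cycle 1 Day 15 row to values from a floor chosen by the clinical team up to below 5.0 mg/dL, and stop both measures under that floor. The entry limit of 2.5 mg/dL is one candidate.

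**Cost.** One sentence, one note and one edited row; no new visits or CRF fields. The downside is a small risk of overshoot, which the stop rule limits and the scheduled phosphorus draws would monitor. From Cycle 3 those draws fall only on Day 1 of each cycle, so it would help to state that the weekly follow-up in Section 6 applies while phosphate is being given; this could mean an occasional additional draw for a treated subject.
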